Chemistry (Serum or plasma)	X	X	(X)	X	X	X	X	X		Within 24 hours prior to treatment on D1 of each cycle, any time on C1D8 and C1D15, and as clinically indicated. Additional collection for phosphorus only at C1D4.	
Urinalysis (Urine dipstick)	X	X				X	X	X			
Pregnancy test	X	X				X	X	X		Serum pregnancy test required for WOCBP at screening and end of treatment; serum or urine pregnancy test required at all other timepoints.	
Blood PK Sampling (Required)						X				Blood samples (1 mL) collected C2D1 pre-dose and at 1h and 3h (±30 min) post-dose. Additional samples collected pre-dose on C3D1 and C4D1.	
Blood PK Sampling (Optional)		Blood samples (minimum 1 mL) collected any day if needed, prior to dose and 1, 2, 3, 4, 6, and 24 hours post-dose.									See also Section 9.13.1
Blood and CSF PK Sampling (Blood, CSF; Optional) (Group 5 only)						(X)				Blood and CSF samples (minimum 1 mL of whole blood and CSF each) collected 2-4 hours after dose on C2D1. See also Section 9.13.1	
ctDNA blood samples	X						(X)			Minimum of 20 mL whole blood at screening (mandatory) and EOT (optional).	

	Screening Period (Within 28 Days Prior to First Dose)	Treatment Period (1 cycle = 21 days)				Safety Follow-up		Survival Follow-up Period	Notes
		Cycle 1			Cycles ≥2	End of Tx (+0-7 days)	30 (±3) days After Last		
		Day 1	Day 4 (±1d)	Day 8 (±3d)	Day 15 (±3d)				
CCI									
Prior & concomitant medications, AE assessments	X	—————→				X	X		Collect from the time informed consent (ICF) is signed through 30 days after administration of the last dose of TAS-120.
Tumor assessments / scans	X					X	X	(X)	
Perform the same tumor assessments/scans obtained at screening at the end of every 2 cycles (up to +2 weeks) up to Cycle 4. Thereafter tumor assessments may be performed every 3 cycles (± 7 days), or as clinically indicated, until radiologic disease progression or initiation of new anticancer therapy (whichever occurs first).
 
At EOT, tumor assessment must be performed if the prior scan was performed ≥9 weeks prior to discontinuation of treatment if the patient discontinued for reasons other than radiologic disease progression. See also Section 9.17.
 
After EOT, patients who discontinued for reasons other than radiologic disease progression should continue to receive tumor assessments every 3 cycles (± 7 days), or as clinically indicated, until radiologic disease progression or initiation of new anticancer therapy (whichever occurs first).

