Height and Weight		X	X			X	X	X	Height at screening only.		
Ophthalmological examination		X				(X)	X	X	At screening and 4-6 weeks after first dose; additional on-study evaluation as needed due to local requirements, physician judgment, and/or symptoms or signs of mineral deposits.		
Neurological examination		X	(X)			(X)	X	X	As clinically indicated after screening, using same methods used at screening.		
ECOG performance status		X	X			X	X	X	Within 24 hours prior to dosing on D1 of each cycle.		
12-Lead Electrocardiogram		X	X			X	X	X	At screening and 2 hours (±15 minutes) after dosing on D1 of each cycle.		

	Pre-Screening	Screening Period (Within 28 Days Prior to First Dose)	Treatment Period (1 cycle = 21 days)					Safety Follow-up		Survival Follow-up Period	Notes
			Cycle 1				Cycles ≥2	End of Tx (+0-7 days)	30 (±3) days After Last		
			1	Day 4 (±1d)		8 (±3d)	15 (±3d)				
Hematology and coagulation		X	X		X	X	X	X		Within 24 hours prior to treatment on D1 of each cycle, any time on C1D8 and C1D15, and as clinically indicated.	
Chemistry (Serum or plasma)		X	X	(X)	X	X	X	X		Within 24 hours prior to treatment on D1 of each cycle, any time on C1D8 and C1D15, and as clinically indicated. Additional collection for phosphorus only at C1D4.	
Urinalysis (Urine dipstick)		X	X			X	X	X			
Pregnancy test		X	X			X	X	X		Serum pregnancy test required for WOCBP at screening and end of treatment; serum or urine pregnancy test required at all other timepoints.	
Blood PK Sampling (Required)						X				Blood samples (1 mL) collected C2D1 pre-dose and at 1h and 3h (±30 min) post-dose. Additional samples collected pre-dose on C3D1 and C4D1.	
ctDNA blood samples		X					(X)			Minimum of 20 mL whole blood at screening (mandatory) and EOT (optional).	
CCI											
Prior & concomitant medications, AE assessments	X	X	—————→				X	X			Collect from the time main informed consent is signed through 30 days after administration of the last dose of TAS-120 or until the start of new anticancer therapy, whichever is earlier. AEs directly associated with a pre-screening procedure should be reported as described in Section 11.1.

	Pre-Screening	Screening Period (Within 28 Days Prior to First Dose)	Treatment Period (1 cycle = 21 days)					Safety Follow-up		Survival Follow-up Period	Notes
			Cycle 1				Cycles ≥ 2	End of Tx (+0-7 days)	30 (± 3) days After Last		
			1	Day 4 ($\pm 1d$)		8 ($\pm 3d$)	15 ($\pm 3d$)				

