7.1.3. Study Duration

Safety monitoring will begin from the time the main study informed consent form (ICF) is signed and will continue for 30 days after the last dose of TAS-120 or until the initiation of another anticancer therapy, whichever occurs first.

Patients will receive study treatment until disease progression, occurrence of intolerable side effects, discontinued from treatment by the investigator, withdrawal of consent, or other criteria for discontinuation is met (see [Section 7.3](#), Discontinuation Criteria). A patient is considered discontinued from study treatment when TAS-120 is discontinued.

For the Phase 1 Expansion part of the study, patients in each treatment group should be followed for survival for up to 12 months after the last patient enrolled in that group.

For Phase 2, patients should be followed for survival for up to 18 months after the last patient enrolled in this phase of the study.

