9.16. Adverse Event Assessment

Patients will be monitored for any untoward medical events (AEs or SAEs) from the time the main study ICF is signed through 30 days after last dose of TAS-120 or until the start of new antitumor therapy, whichever is earlier. For the Phase 2 part of the study, any AEs or SAEs that occur after the signing of pre-screening consent and are directly associated with a pre-screening procedure (i.e., fresh tumor biopsy) should be reported as described in Section 12.1. For AEs and SAEs that occur between signing the pre-screening consent and main study ICF, there is no need to record those that are unrelated unless it is mandatory by local regulations.

Serious AEs should be reported to Taiho Oncology, Incorporated (TOI) Pharmacovigilance or its designee. If serious medical occurrences or deaths **outside** the 30-day follow-up period are

reported to or observed by the investigator that he/she believes are related to the administration of the TAS-120, it is the investigator's responsibility to report this occurrence to TOI Pharmacovigilance or its designee. See [Section 11.1.1](#), Adverse Events, and [Section 11.1.2](#), Serious Adverse Events, for definitions and detailed reporting of AEs and SAEs.

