11. REPORTING SAFETY INFORMATION

11.1. Adverse Events/Serious Adverse Events

11.1.1. Adverse Events

An AE is any untoward medical condition that occurs in a patient from the time the ICF is signed and does not necessarily have a causal relationship with the use of the product.

A complete and specific clinical diagnosis should be provided for the AE verbatim term. If a diagnosis is not available, then signs and symptoms should be reported. The CTCAE (version 4.03) terms are to be used to assess severity and provide the grade for each AE that is reported.

For definitions and reporting of pregnancy, overdose, and medication errors, refer to [Section 11.1.5](#), Pregnancy, [Section 11.1.6](#), Overdose, and [Section 11.1.7](#), Medication Errors, respectively.

Any untoward medical event that occurs outside the period of patient follow-up (30 days after the last dose of study drug or until the start of new antitumor therapy, (whichever is earlier) is not considered an AE.

Symptoms or laboratory or instrumental (e.g., electrocardiographic) abnormalities of a pre-existing disease, such as cancer or other diseases, should not be considered an AE. However, occurrences of new symptoms as well as worsening of pre-existing medical conditions are considered AEs. In addition, **a new laboratory or instrumental abnormality that has a clinical impact on a patient (e.g., resulting in study drug dose reduction, treatment delay, treatment discontinuation) is considered an AE, unless it is considered part of clinical manifestations to a clinical diagnosis that is already reported as an AE.**

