# 5. STUDY PERIODS, TREATMENT REGIMENS, AND POPULATIONS FOR ANALYSIS

#### 5.1. Study Periods

The study periods are defined in the table 4 below.

**Table 4.** Definition of Study Periods for Analysis

Period	Definition
Baseline / Screening	From the day of ICF signature (up to 28 days before first dose) to the day and time of the first dose of study drug.
On-treatment	From the date of first dose of study therapy through 30 days after the last dose of study therapy. Unless otherwise specified, the on-treatment period will be the basis for the summaries of safety.

Abbreviations: ICF=informed consent form.

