#### 7.2. Post-Baseline Period

On-treatment AEs will be defined as AEs with an onset date and time on or after the date-time of the first dose of study drug (or with an onset date on or after the day of first dose of study treatment if time is not collected or is missing). An AE will be counted as on-treatment if the event occurred within 30 days of the last dose of study treatment.

On-treatment evaluations (laboratory tests, vital signs) will be defined as evaluations taken after the day (and time, if collected and not missing) of first dose of study treatment. An evaluation will be counted as on-treatment if it occurred within 30 days of the last dose of study treatment.

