#### 7.4. Time-to-Onset Definition

Time-to-onset of AESI (any grade) for a specific category (for example, pulmonary events, gastrointestinal events) is defined as the time between the day of the first dose of treatment and the onset date of the earliest AESI (of any grade) in this category.

If the subject did not experience an AESI (of any grade) in the category, time-to-onset will be censored at the maximum follow-up time of each subject in their respective treatment group (that

is, for subjects without an event, follow-up time is defined from first dosing date up to last dosing date +30 days if subjects are off treatment and followed for at least 30 days, otherwise it is defined up to the last known alive date). The resulting Kaplan-Meier plot will represent the cumulative rate of the AESI (any grade) in the category over time.

Time-to onset of AESI (Grade 3-5) for a specific category is defined similarly but restricted to Grade 3-5 AESI.

Time-to onset of study treatment-related (Grade 3-5 or any grade) AESI for a specific category is defined similarly but restricted to study treatment-related AESI.

Time-to onset for a specific subcategory is defined similarly but restricted to events in this subcategory.

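### The protocol text ends AE follow-up at new anticancer therapy, but the Expansion schedule and the on-treatment and AESI censoring rules of both SAPs have no such stop

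*SAP*

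**What the plan says.** **Protocol text, all parts.** Section 7.1.3 says that safety monitoring "will continue for 30 days after the last dose of TAS-120 or until the initiation of another anticancer therapy, whichever occurs first". Section 9.16 has patients monitored for AEs "through 30 days after last dose of TAS-120 or until the start of new antitumor therapy, whichever is earlier". Section 11.1.1 adds that an untoward event outside the period of 30 days "or until the start of new antitumor therapy, (whichever is earlier) is not considered an AE". Section 11.1.2 limits SAE follow-up in the same way.

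**Schedules.** The Phase 2 schedule (Protocol Table 2, repeated as Table 1 of the Phase 2 SAP) carries the stop: "administration of the last dose of TAS-120 or until the start of new anticancer therapy, whichever is earlier". The Expansion schedule (Protocol Table 1, repeated in the Expansion SAP) does not: "Collect from the time informed consent (ICF) is signed through 30 days after administration of the last dose of TAS-120".

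**Analysis rules.** Section 5.1 of both SAPs defines the on-treatment period as "From the date of first dose of study therapy through 30 days after the last dose of study therapy". Phase 2 SAP 7.2 and Expansion SAP 8.2 apply it to events: "An AE will be counted as on-treatment if the event occurred within 30 days of the last dose of study treatment". The same sections treat laboratory and vital-sign evaluations alike, and 6.5.2.5 of each SAP uses the same 30 days. For patients without an AESI, Phase 2 SAP 7.4 sets the censoring time: "follow-up time is defined from first dosing date up to last dosing date +30 days if subjects are off treatment". It requires that the patient was also followed for at least 30 days, and otherwise uses the last date known alive. Expansion SAP 8.4 has the same two branches.

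**The concern.** The window in which AEs are collected and the window in which they are analysed should be the same. Here they differ, and the difference works in opposite directions in the two parts.

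In the Expansion, Table 1 tells sites to keep recording AEs to day 30 even if the patient has moved to another treatment, and the SAP then counts those AEs as on-treatment. Toxicity of the next therapy would appear in the all-cause tables for TAS-120, although Protocol 11.1.1 says that such an event is not an AE of this study.

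In Phase 2, sites stop recording at new therapy, but the time-to-onset analysis keeps the patient in the risk set beyond that date. Days on which no one was asked to record AEs are treated as days without an AESI. This pulls the Kaplan-Meier cumulative incidence of AESIs, including hyperphosphatemia, downward.

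Expansion sites also hold two conflicting instructions within one protocol.

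**Working it through.** No figure in the plan depends on this point, so there is nothing to reproduce. The check is a comparison of the windows, followed by an illustration of scale.

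**Step 1. The windows side by side**

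| Place | End of window | Stop at new therapy? |
|---|---|---|
| Protocol 7.1.3, 9.16, 11.1.1, 11.1.2 | last dose + 30 days | yes |
| Protocol Table 2; Phase 2 SAP Table 1 | last dose + 30 days | yes |
| Protocol Table 1; Expansion SAP Table 1 | last dose + 30 days | no |
| Expansion SAP 5.1, 6.5.2.5, 8.2 | last dose + 30 days | no |
| Phase 2 SAP 5.1, 6.5.2.5, 7.2 | last dose + 30 days | no |
| Expansion SAP 8.4; Phase 2 SAP 7.4 (AESI censoring) | last dose + 30 days, or last date known alive | no |

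The Phase 2 SAP therefore disagrees with its own schedule. Neither the list of changes in Expansion SAP section 7 nor the revision history in Phase 2 SAP section 9 mentions a wider analysis window. The Dose Escalation SAP has the same split: its section 4.1 has the stop, while its AE schedule footnote and sections 5.1.1 and 10.3 do not.

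**Step 2. An Expansion patient (illustrative days)**

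Take the last dose as day 0, new therapy on day 15 and a Grade 3 event on day 20. Under Protocol 11.1.1 this is not an AE. Under Table 1 it is recorded. Under Expansion SAP 8.2, 20 is within 30, so it is on-treatment and enters the all-cause tables of 6.5.2.5. It enters the treatment-related tables only if it is marked related or if the relationship is missing.

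**Step 3. A Phase 2 patient with the same dates and no AESI**

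AE collection ends on day 15. Under SAP 7.4 there are two possibilities:

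- If the patient counts as followed for at least 30 days, censoring is at day 30, and 30 − 15 = 15 days are unobserved. The rule does not say that the follow-up must be for AEs, so survival follow-up (Protocol 9.21) could satisfy it.
- If the patient does not, censoring is at the last date known alive. If followed is read as followed for AEs, that date can come from a later survival contact, and the unobserved stretch can run past day 30.

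Neither branch uses the start date of new therapy.

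**Step 4. Scale, on assumptions**

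Let N = 100 patients (the approximate Phase 2 size, Protocol 12.3.3), f = share starting new therapy within 30 days of last dose, and t = mean start day. Neither f nor t is in the documents. Unobserved days within the 30-day tail are U = N × f × (30 − t). This is an upper bound for the tail, because it takes all patients as off treatment and AESI-free.

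| f | t = 20 | t = 10 |
|---|---|---|
| 10% | 100 × 0.1 × 10 = 100 | 100 × 0.1 × 20 = 200 |
| 30% | 100 × 0.3 × 10 = 300 | 100 × 0.3 × 20 = 600 |
| 50% | 100 × 0.5 × 10 = 500 | 100 × 0.5 × 20 = 1,000 |

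The tail holds 100 × 30 = 3,000 patient-days, so the range is 100/3,000 = 3.3% to 1,000/3,000 = 33.3% of it. As a share of treatment plus tail it is smaller. With an assumed mean treatment of 90 days it is 100/12,000 = 0.8% to 1,000/12,000 = 8.3%. With 270 days it is 100/30,000 = 0.3% to 1,000/30,000 = 3.3%.

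For 100 Expansion patients whose sites followed Table 1 in full, an assumed rate of 1 AE per patient-month on the next therapy would add 100/30.4375 = 3.3 to 1,000/30.4375 = 32.9 AE records.

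**The case against.** The strongest reply is that the protocol already settles the matter. Sections 9.16 and 11.1.1 apply to every part, and an event after new therapy is by definition not an AE. The SAP rules start from a recorded AE and classify it; they do not widen collection. On this view the only conflict is one note on a schedule row that AEs share with medications, which are indeed collected through the 30-day visit (Protocol 9.15). This largely stands for Phase 2 counting, because sites there are told to stop. It does not settle the Expansion, where the note tells sites to record the event and no derivation rule removes it. Nor does it answer the AESI censoring rules.

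A second reply is that Protocol 9.20 places the safety visit before new therapy, and repeat testing stops at new treatment (11.2.2). This stands for scheduled laboratory values, whose exposure is limited. It also confirms that the days after new therapy are largely unobserved.

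Some stronger readings are tempting, and the documents do not support them:

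- *That next-therapy toxicity enters liver tables in the Expansion.* Expansion SAP 6.5.3 has no hepatic abnormality analysis. Those tables are in Phase 2 SAP 6.5.3, where AE collection stops at new therapy and 9.20 also applies.
- *That pooled safety would mix two windows.* Each part has its own SAP, and these documents plan no pooled safety analysis.
- *That Grade 3 or higher incidence is inflated by 4 to 8 points.* This multiplies an assumed 20% to 40% starting new therapy by an assumed 20% with a new event (0.2 × 0.2 and 0.4 × 0.2). All inputs are assumed. A patient is counted once at the highest grade, so anyone with an earlier Grade 3 or higher event adds nothing. The product is a ceiling under its own assumptions, not an estimate.
- *That next-therapy events would be labelled as caused by TAS-120.* The all-cause tables make no causal claim, and an event judged not related stays out of the related tables.

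**Conclusion.** The contradiction is real and should be reconciled. Followed as written, the Expansion schedule and SAP can count AEs on the next therapy in the all-cause on-treatment tables. The Phase 2 AESI time-to-onset rule can keep patients in the risk set on days without AE collection.

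The size cannot be determined, because no document gives the share or timing of new therapy within 30 days; the ranges above rest wholly on assumed values. The effect on a Kaplan-Meier curve also depends on whether other patients have their first AESI at the same times since first dose, which is not known either.

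The consequence is confined to descriptive safety summaries. ORR, its confidence interval and the sample size do not depend on this window. It is a cheap correction worth making before the safety tables are produced, not a threat to the primary conclusion.

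**What to change.** Use the protocol text's window everywhere, so that follow-up ends at day 30 after last dose or at the start of new anticancer therapy if that is sooner:

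- **Protocol Table 1 and its copy in the Expansion SAP:** add the stop to the AE part of the note only. Medications stay collected through the 30-day visit, as in 9.15.
- **On-treatment definitions:** add it to Expansion SAP 5.1, 6.5.2.5 and 8.2, and to Phase 2 SAP 5.1, 6.5.2.5 and 7.2.
- **AESI censoring:** add it to both branches of Phase 2 SAP 7.4 and of Expansion SAP 8.4.
- **Deaths:** keep reporting them through 30 days, as Protocol 11.1.3 requires, and show separately those that follow new therapy.

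The cost is wording plus one date in the derivations. Protocol 9.15 already collects the start of new anticancer therapy during the 30-day follow-up period, so no new data are needed.

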#### 7.3. AESI Definition and Conventions

The AESI consist of a list of preferred terms grouped by specific category (for example, pulmonary events, gastrointestinal events categories) and/or by subcategory (for example, diabetes). These categories and subcategories are defined based on MedDRA, and the list that is most current at the time of analysis will be used. In addition, changes may be made to this list with each new version of MedDRA.

#### 7.4. Time-to-Onset Definition

Time-to-onset of AESI (any grade) for a specific category (for example, pulmonary events, gastrointestinal events) is defined as the time between the day of the first dose of treatment and the onset date of the earliest AESI (of any grade) in this category.

If the subject did not experience an AESI (of any grade) in the category, time-to-onset will be censored at the maximum follow-up time of each subject in their respective treatment group (that

is, for subjects without an event, follow-up time is defined from first dosing date up to last dosing date +30 days if subjects are off treatment and followed for at least 30 days, otherwise it is defined up to the last known alive date). The resulting Kaplan-Meier plot will represent the cumulative rate of the AESI (any grade) in the category over time.

Time-to onset of AESI (Grade 3-5) for a specific category is defined similarly but restricted to Grade 3-5 AESI.

Time-to onset of study treatment-related (Grade 3-5 or any grade) AESI for a specific category is defined similarly but restricted to study treatment-related AESI.

Time-to onset for a specific subcategory is defined similarly but restricted to events in this subcategory.

#### 7.5. Time-to-Resolution Definition

In order to derive the time-to-resolution, overlapping or contiguous AESI within a specific category will be collapsed into what will be termed "clustered" AESI. For example, if a subject (without pre-treatment AE) experienced an AE from 01 January to 05 January, another AE (with different PT but within same category) from 06 January to 11 January, and the same AE from 10 January to 12 January, these will be collapsed into one clustered AESI from 01 January to 12 January. Table 13 summarizes key derivation steps for each type of clustered select AEs. Algorithm for collapsing multiple records of adverse event is summarized in Section 7.6.

Time-to-resolution of AESI (any grade) for a specific category is defined as the longest time from onset to complete resolution or improvement to the grade at baseline among all clustered AESI in this category experienced by the patient. Events which worsened into Grade 5 events (death) or have a resolution date equal to the date of death are considered unresolved. If a clustered AESI is considered to be unresolved, the resolution date will be censored to the last known date alive. Improvement to the grade at baseline implies that all different AE events in the clustered AESI should at least have improved to the corresponding (that is, with same preferred term) baseline grade. This measure is defined only for subjects who experienced at least one AESI in the specific category.

The time-to-resolution of AESI (Grade 3-5) for a specific category is defined similarly with an onset date corresponding to a Grade 3-5 AESI.

Time-to-resolution of study treatment-related AESI (any grade or Grade 3-5) is defined similarly but restricted to study treatment-related AESI.

Time-to-resolution for a specific subcategory is defined similarly but restricted to events of this subcategory.

**Table 13.** Derivation of Clustered AESI

Type of clustered select AE	Derivation
Any grade	Collapse any on-treatment AESI from the same category
Study treatment-related of any grade	Collapse any on-treatment, study treatment-related AESI from the same category
Grade 3-5	Collapse any on-treatment AESI from the same category. Resolution will be based on the onset date of the earliest Grade 3-5 records (if no Grade 3-5 record, clustered AESI is excluded)
Study treatment-related of Grade 3-5	Collapse any on-treatment, study treatment-related AESI from the same category. Resolution will be based on the onset date of the earliest Grade 3-5 record (if no Grade 3-5 record, clustered AESI is excluded)

Abbreviations: AE=adverse event; AESI=adverse event of special interest.

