- 6) AEs leading to study treatment termination, overall and by system organ class and preferred term. Additional summary by system organ class, preferred term and grade (including Total and >= grade 3 categories) will also be generated.
- 7) AEs with outcome of deaths, overall and by system organ class and preferred term

The time to onset of some special AEs of interest in the study may be summarized if appropriate.

Severity of hyperphosphatemia will be graded based on serum phosphate levels as illustrated in Table 8 using identical derivation criteria as specified in the protocol (Protocol section 8.1.3.1.1,).

In addition, hyperphosphatemia toxicities grading based on CTCAE v5.0 will also be provided using the derivation criteria presented in Table 9.

Table 8. Hyperphosphatemia Toxicity Grading based on serum phosphate levels as specified in Protocol \*

	Grade 1	Grade 2	Grade 3	Grade 4
Serum Phosphorus Result	( 0 /	$5.5 \le P \le 7.0 \text{ (mg/dL)}$	$7.0 < P \le 10.0 \text{ (mg/dL)}$	P > 10.0  (mg/dL)
( /17 1 1/7)		$1.78 \le P \le 2.26 \text{ mmol/L}$	$2.26 < P \le 3.23 \text{ (mmol/L)}$	P > 3.23 (mmol/L)

\* Section 8.1.3.1.1, protocol amendment 9

Table 9. Hyperphosphatemia Toxicity Grading per CTCAE v5.0 and derivation criteria

	Grade 1	Grade 2	Grade 3	Grade 4	Grade 5
CTCAE v5.0 criteria	Laboratory finding only and intervention no indicated	Noninvasive intervention indicated	significant but no		Death
Derivation criteria	Serum phosphat > ULN	> ULN AND concomitant	Serum phosphate > ULN AND Concomitant therapy with phosphate binder AND SAE ohyperphosphatemia/related toxicity*	Serum phosphate > ULN  AND  Concomitant therapy with phosphate binder  AND  SAE ohyperphosphatemia/ related toxicity with immediately life threatening consequences*	hyperphosphatemia or related toxicity*

\* as assessed by the sponsor

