#### **Time to Resolution:**

Time-to-resolution of selected AESI, including hyperphosphatemia, will be summarized separately for each category / subcategory:

- Time to resolution of AESI
- Time to resolution of AESI of Grade  $\geq 3$

Time-to-resolution analyses are restricted to treated patients who experienced the specific events.

The following summary statistics will be reported: percentage of subjects who experienced the specific events, percentage of subjects with resolution of the longest AESI, median time-to resolution and to  $\leq$  Grade 2 along with 95% CI (derived from Kaplan-Meier estimation, if estimable) and ranges.

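### The Kaplan-Meier median time to AESI resolution censors patients who die with the event open, which biases it toward faster resolution; the effect is small unless such deaths are common

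*SAP*

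**What the plan says.** Phase 2 SAP 7.5 (Time-to-Resolution Definition) sets two rules in sequence. The first classes the event: "Events which worsened into Grade 5 events (death) or have a resolution date equal to the date of death are considered unresolved". The second says what happens to it: "If a clustered AESI is considered to be unresolved, the resolution date will be censored to the last known date alive". For a patient who has died, that date is in effect the date of death. The rule covers an AESI that becomes Grade 5 and also a non-fatal AESI still open when the patient dies of something else, including the cancer.

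Phase 2 SAP 6.5.2.6 (Time to Resolution) defines the analysis set: "Time-to-resolution analyses are restricted to treated patients who experienced the specific events". Its listed outputs are the percentage with the event, the "percentage of subjects with resolution of the longest AESI", and the median "along with 95% CI (derived from Kaplan-Meier estimation, if estimable) and ranges". The Kaplan-Meier graph in that section is for time to onset; none is listed for time to resolution.

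Expansion SAP 8.5 carries the same classing and censoring rules, and Expansion SAP 6.5.2.6 the same Kaplan-Meier median. Neither SAP names a competing-risk method for this analysis.

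**The concern.** Kaplan-Meier censoring is valid when a censored patient could still have the event and would have it at the rate of those who remain at risk. Death with the AESI open breaks that condition, because resolution has become impossible. Classing the event as unresolved is the cautious choice, but censoring it at death removes that caution from the median: the patient leaves the risk set and is implicitly assigned the remaining patients' resolution rate.

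The bias has one direction, toward a shorter median, and it grows with the share of AESIs open at death. The same SAP handles death differently elsewhere: it is an event for PFS (Table 6) and counts as deterioration in the PRO time-to-deterioration analysis (6.6.2). At stake is how quickly readers of the safety section believe these toxicities clear.

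**Working it through.** The plan states no time-to-resolution figure, so there is nothing to reproduce. The check compares the planned estimator with a competing-risk estimator under stated assumptions.

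**Inputs from the documents.** Fatal or open-at-death AESIs are unresolved and censored at the last date known alive (7.5); the estimator is Kaplan-Meier (6.5.2.6).

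**Inputs assumed, not in the documents.** A share f of affected patients die with the AESI open. The other 1 − f resolve with an exponential median of 21 days, so λ = ln 2/21 = 0.0330 per day. Deaths follow an exponential with median 14 days, so δ = ln 2/14 = 0.0495 per day. There is no other censoring in this first comparison.

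**SAP rule.** With deaths censored, the hazard that Kaplan-Meier estimates is

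h(t) = (1 − f)λe^(−λt) / [(1 − f)e^(−λt) + f e^(−δt)].

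The median is the t at which the integral of h from 0 to t equals ln 2 (solved numerically).

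**Death as a competing event.** CIF(t) = (1 − f)(1 − e^(−λt)), so the median is −ln(1 − 0.5/(1 − f))/λ. At f = 10% this is 0.8109/0.0330 = 24.6 days; at f = 20%, 0.9808/0.0330 = 29.7 days.

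| Share open at death (assumed) | Kaplan-Meier median, days | Cumulative-incidence median, days | Difference |
|---|---|---|---|
| 2% | 21.4 | 21.6 | about 0.2 |
| 5% | 21.9 | 22.6 | 0.7 |
| 10% | 22.9 | 24.6 | 1.7 |
| 20% | 25.3 | 29.7 | 4.4 |

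**Second model.** Take constant cause-specific hazards with a Kaplan-Meier median of 14 days: λ = ln 2/14, μ = λf/(1 − f), CIF(t) = (1 − f)(1 − e^(−(λ+μ)t)). The median moves from 14 days to 14.1 (2%), 14.3 (5%), 14.7 (10%), 15.8 (20%) and 17.7 (30%). The direction is the same and the shifts are smaller.

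**Small samples.** In a constructed set of 20 AESIs, the two medians were identical with 1, 2 or 4 deaths, and 27 versus 30 days with 6.

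**A tempting alternative remedy.** Suppose deaths are simply kept in the risk set to the end of the time axis. Add random censoring of patients still under observation with a median of 30 days (assumed, γ = ln 2/30) and take f = 20%. Observed deaths then add fδ/(δ + γ)·(1 − e^(−(δ+γ)t)) to the risk set at full weight, while everyone else is thinned by e^(−γt). The median becomes 31.5 days against a true 29.7, and 62.8% are resolved at day 60 against a true 69.0%. This overshoots in the opposite direction.

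**The case against.** The strongest reply is that little of the planned reporting is touched.

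- A reader might infer that resolution is also made to look more complete. The documents do not support that. The only completeness measure listed is the crude "percentage of subjects with resolution of the longest AESI", in which a fatal or open-at-death AESI counts as not resolved. A Kaplan-Meier resolution curve or fixed-day rate would overstate completeness, but none is planned.
- A reader might infer that fatal events are hidden. They are not. Phase 2 SAP 6.5.2.5 lists a table of "AEs with outcome of deaths, overall and by system organ class and preferred term", AESIs are tabulated by worst grade and listed by patient, and all deaths are summarised by reason.
- The fatal share may be low. Hyperphosphatemia is the only AESI named for this analysis, and the protocol's grading of it by serum phosphorus stops at Grade 4; Grade 5 appears only in the supplementary CTCAE v5.0 derivation.
- Sampling noise is larger than the bias. With 20 affected patients, the simulated standard deviation of the Kaplan-Meier median is roughly 7 to 8 days at a 5% or 10% share and somewhat more at 20%. The bias is then about 0.1, 0.2 and 0.5 of a standard deviation.

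All of this stands as a limit on size and scope. It does not make the censoring rule correct. The rule also catches non-fatal AESIs open at death from any cause, so the affected share can exceed the Grade 5 share, and the AESI list is open-ended (Phase 2 SAP 7.3 gives pulmonary events as an example).

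**Conclusion.** The point holds for the Kaplan-Meier median time to resolution and its 95% CI in both SAPs: the stated rule biases them toward faster resolution. It does not extend to the crude percentage resolved, to the reporting of deaths, or to the ORR analysis and its decision rule.

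Under the 21-day and 14-day assumptions the shift is under one day at a 5% share or below, about 1.7 days at 10% and 4.4 days at 20%. The true share is not in the documents, so the size cannot be settled from them; the effect is small unless deaths with an open AESI are common. As this is a descriptive safety summary with no hypothesis attached, severity is low.

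**What to change.** In Phase 2 SAP 7.5 and Expansion SAP 8.5:

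- Treat death with the AESI unresolved as a competing event.
- Read the median and its 95% CI from the Aalen-Johansen cumulative incidence of resolution, stated as not reached if the curve stays below 50%.
- Keep ordinary censoring for living patients whose AESI is unresolved.
- Report the number of deaths with an unresolved AESI beside the median.
- Apply the same rule to the median time to Grade 2 or lower in Phase 2 SAP 6.5.2.6, if it is derived from the same analysis.

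Do not replace the rule by holding deaths in the risk set to the end of follow-up; with other censoring present, that makes the median too long.

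The cost is a short wording change in each SAP and minor programming, with no new data. The reported median becomes slightly longer.
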